4.1.4 Exploratory Endpoints

Any comparisons between groups (Cingal, Monovisc, TH), within groups and / or time points (from baseline through to 39 weeks) not described in the primary or secondary endpoints may be presented in the exploratory endpoints including:

- EuroQoL (EQ-5D)
- WOMAC Pain Score (100mm VAS)
- OMERACT-OARSI
- Total WOMAC
- WOMAC Stiffness Score
- WOMAC Physical Function Score
- Patient Global Assessment
- Evaluator Global Assessment
- Range of Motion
- Rescue Medication Usage: Difference in analgesic use measured by number of pills taken between visits will be compared between treatment groups descriptively.
- Number of Subjects Considered Treatment Failures: Treatment Failure: A subject who undergoes a procedure or uses a medication (other than the rescue medication) for the treatment of OA in the index knee at any time after the study injection through the 12 week visit.

For the exploratory analyses, the continuous variables will be analyzed via an analysis of variance and contrasts used to assess the prescribed comparisons. For the discrete variables, a Fisher's exact test will be used to assess the desired comparisons.

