2 DEFINITIONS

Baseline: The assessments performed prior to the study injection after the Screening Visit.

Blinded Evaluator: The Blinded Evaluator will be a physician, research nurse, registered physiotherapist or physician assistant trained by the PI to perform the assessments outlined in the protocol. The Blinded Evaluator will complete the physical evaluation of both knees, range of motion (ROM) assessment of both knees, and the Evaluator Global Assessment.

End of Study: End of study is defined as the last subject's last visit.

Enrolled: A subject who has signed the informed consent form (ICF) is enrolled.

Index Knee: The knee that meets the eligibility criteria for treatment. The index knee may also be termed the "study knee". In subjects with bilateral knee Osteoarthritis (OA), where both knees meet eligibility criteria, the more symptomatic knee is the index knee.

Ethics Committee (EC): EC refers to an independent body (e.g. Research Ethics Boards, Independent Ethics Committees) whose responsibility is to ensure the protection of rights, safety and well-being of human subjects involved in a trial. Committees with these responsibilities will be referred to in this document as Ethics Committees.

Rescue Medication: Acetaminophen/paracetamol will be distributed as the rescue medication. It is the only medication that should be taken for knee pain during the entire study. Rescue medication will be discontinued at least 48 hours prior to Baseline and all follow-up visits.

Treating Physician: The Treating Physician will most often be the Principal Investigator (PI). He/she will administer the Cingal®, Monovisc® or steroid injection but will not participate in the efficacy evaluation.

Treatment Failure: A subject who undergoes a procedure or uses a medication (other than the rescue medication) for the treatment of OA in the index knee at any time after the study injection through the 39 week visit.

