3 STUDY SYNOPSIS

Title	Extension Study to Cingal 16-02: Trial Extension to 39 Week Follow Up in the Randomized, Double-Blind, Active Comparator Controlled, Multi-Center Study of a Single Injection Cross-Linked Sodium Hyaluronate Combined with Triamcinolone Hexacetonide (Cingal) to Provide Symptomatic Relief of Osteoarthritis of the Knee
Study Objective	To evaluate the efficacy and safety of a single injection of Cingal for relief of joint pain at 39 week follow up in subjects with Osteoarthritis (OA) of the knee who have not responded to conservative treatment.
Investigational Product	Subjects enrolled in Cingal 17-02 will not receive an injection. For reference only, the investigational product utilized in Cingal 16-02 was: Cingal : A chemically cross-linked sodium hyaluronate supplied as a 4-mL unit dose with a nominal 18 mg of triamcinolone hexacetonide (TH) in a 5-mL glass syringe.
Comparator Product	Subjects enrolled in Cingal 17-02 will not receive an injection. For reference only, the comparator products utilized in Cingal 16-02 were: Triamcinolone Hexacetonide (TH) : 20 mg/ml supplied as 1 mL unit dose in a glass ampoule. Monovisc® : A chemically cross-linked sodium hyaluronate supplied as a 4-mL unit dose in a 5-mL glass syringe.
Mode of Delivery	For reference only, the mode of delivery in Cingal 16-02 was: Cingal, Triamcinolone Hexacetonide, or Monovisc will be injected into the intraarticular (IA) space of the index knee using an 18-21 gauge needle.
Study Design	Multi-center, randomized, double-blind, parallel group, 3-arm, active comparator controlled study
Phase	Phase III
Sample Size	A total of 576 subjects will be enrolled. This equates to 256 subjects injected with Cingal, 256 subjects injected with Monovisc and 64 subjects injected with TH. All subjects who meet enrollment criteria and completed the 26 week follow up in Cingal 16-02 will have the option to participate in the sub-study.
Study Duration	The entire sub-study duration will be an additional 13 weeks. The follow up visit will be scheduled at 39 weeks post treatment.

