10 STUDY PROCEDURES

10.1 Schedule of Events

	Pre-Treatment	Treatment		Post-Treatment Follow-Up Visits						17-02 Follow-Up Visits	
		Day 0 (7-14 days after screening visit)		1 week	3 weeks	6 weeks	12 weeks	18 weeks	26 weeks	Consent	39 Weeks
Assessments	-7 to -14 Days	Day 0 (7-14 days after screening visit)		1 week	3 weeks	6 weeks	12 weeks	18 weeks	26 weeks	Consent	39 Weeks
	Screening	Baseline	Treatment	±3 days			± 1 week				
Informed Consent	X									X	
Demographics Medical History	X										
Physical Exam, Vitals, BMI	X										
Urine / Blood Pregnancy Test	X										
Chemistry/Hematology/Urinalysis	X										
Bilateral Knee X-rays and assessment of K-L	X										
Review of X-rays by Independent Radiologist	X										
Physical Evaluation (Both Knees)	X	X		X	X	X	X	X	X		X
ROM (Index Knee)	X	X		X	X	X	X	X	X		X
ROM (Contralateral Knee)	X	X					X		X		X
WOMAC (Both Knees)	X	X		X	X	X	X	X	X		X
Evaluation of Enrollment Criteria	X	X	X							X	
Stop Analgesics/NSAIDs except Paracetamol	X										
Assess D/C Paracetamol ≥ 48 hours before Visit		X		X	X	X	X	X	X	X	X
Paracetamol Dispense/Pill Count	X	X		X	X	X	X	X	X	X	X
Distribute Subject Diary	X										X
Randomization			X								
Aspiration/ Evaluation of Synovial Fluid			X								
IA Injection			X								
Evaluate Diary		X		X	X	X	X	X	X		X
EuroQol		X		X	X	X	X	X	X		X
Patient Global Assessment		X		X	X	X	X	X	X		X
Evaluator Global Assessment		X		X	X	X	X	X	X		X
Concomitant Medication Assessment				Throughout the study							
Adverse Event Assessment				Throughout the study							

† -Cells in grey indicate assessments conducted only during Cingal 16-02 trial.

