10.2.12.3 Concomitant Medications

A medication is considered concomitant if taken after signing the ICF and up to and including the 39 week follow-up visit. Data on medications will include: medication name, dose, unit, route, frequency, start date, stop date, indication and whether the medication was taken for an AE.

At each study visit, the subject will be asked about any new medications that were started since the last visit. Indications for any new medications during the study period will be recorded as AEs, unless the medications are administered for a pre-existing condition.

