12 STATISTICAL CONSIDERATIONS

The statistical analysis of the study is described in detail in a separate version-controlled prospective Statistical Analysis Plan (SAP). However, the statistical methodology described in this section of the protocol will be the basis for the detailed SAP.

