3.3 EXPLORATORY ENDPOINTS

Any comparisons between groups (Cingal, Monovisc, TH), within groups and / or time points (from baseline through to 39 weeks) not described in the primary or secondary endpoints may be presented in the exploratory endpoints including:

- EuroQol (EQ-5D)
- WOMAC Pain Score (100mm VAS)
- OMERACT-OARSI
- Total WOMAC
- WOMAC Stiffness Score
- WOMAC Physical Function
- Patient Global Assessment
- Evaluator Global Assessment
- Range of Motion
- Rescue Medication Usage
- Number of Treatment Failures due to Additional Procedure or Use of Disallowed Medication

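### SAP 4.1.4 stops counting treatment failures at the 12 week visit, while the protocol counts them through the 39 week visit

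*SAP*

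**What the plan says.** SAP 4.1.4 lists the number of treatment failures among the exploratory endpoints and defines the term there. A failure is a subject who undergoes a procedure or uses a medication other than rescue "for the treatment of OA in the index knee at any time after the study injection through the 12 week visit". The same section sets the test: "For the discrete variables, a Fisher's exact test will be used to assess the desired comparisons".

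Protocol Section 2 (Definitions) defines the term with a different end point: "for the treatment of OA in the index knee at any time after the study injection through the 39 week visit". Protocol Section 12.1.3 repeats that definition with the 39 week visit.

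On the relation between the two documents, Protocol Section 12 states that "the statistical methodology described in this section of the protocol will be the basis for the detailed SAP". SAP 3.3 and the opening of SAP 4.1.4 describe the exploratory comparisons as covering "within groups and / or time points (from baseline through to 39 weeks".

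**The concern.** One endpoint has two definitions in current text, and they differ only in the week number. A programmer working from the SAP and a reader working from the protocol would arrive at different counts.

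The sub-study exists to assess the injection at week 39. Under the SAP wording, nothing that happens between weeks 26 and 39 can count as a failure, so the extension adds no information to this endpoint. A failure table in a 39-week report that stops at week 12 says nothing about added treatment in the later period, and a reader could easily take it to cover the whole follow-up.

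**Working it through.** The plan states no figure for this endpoint, so there is none to reproduce. The check sets the definitions side by side and then measures how much follow-up the SAP window omits.

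**The texts**

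| Source | End of failure window |
|---|---|
| Protocol Section 2 | 39 week visit |
| Protocol Section 12.1.3 | 39 week visit |
| SAP 4.1.4 | 12 week visit |

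The rest of the definition is the same in all three places. The SAP gives no reason for a shorter window, and no other SAP endpoint stops at week 12. The protocol's change table, where legible, lists no change to the failure definition.

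**Follow-up left out**

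- Weeks omitted: 39 − 12 = 27, and 27/39 = 69.2%. The SAP window covers 12/39 = 30.8%.
- Of those 27 weeks, 39 − 26 = 13 are the extension. The other 26 − 12 = 14 are in Cingal 16-02.
- Follow-up visits in Protocol Section 10.1 are at weeks 1, 3, 6, 12, 18, 26 and 39, which is 7. Those at weeks 18, 26 and 39 fall outside the window, so 3 of 7 are lost.

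**Share of failures still counted (illustration)**

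The documents give neither the rate nor the timing of failures, so both are assumed. Let F be the cumulative proportion failing by week 39 and k the shape of a Weibull time-to-failure distribution. The proportion failing by week 12 is

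F12 = 1 − (1 − F)^((12/39)^k),

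and the share counted is F12/F.

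| Timing assumption | F = 5% | F = 10% | F = 20% | F = 30% |
|---|---|---|---|---|
| Constant hazard (k = 1): F12 | 1.57% | 3.19% | 6.64% | 10.39% |
| Constant hazard (k = 1): share counted | 31.3% | 31.9% | 33.2% | 34.6% |

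Over the same range of F, early failures (k = 0.5) give a share of 56% to 60%, and late failures (k = 2) give 10% to 11%.

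As an example, take F = 10%, a constant hazard, the same rate in both arms and every subject followed to week 39:

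- Cingal: 256 × 0.10 = 25.6 failures, of which 256 × 0.0319 = 8.2 are counted.
- TH: 64 × 0.10 = 6.4 failures, of which 64 × 0.0319 = 2.0 are counted.

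Fisher's exact test would then compare about 8 with 2 failures instead of about 26 with 6.

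**Whether the data exist**

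On medication, Protocol Section 10.2.12.3 says: "A medication is considered concomitant if taken after signing the ICF and up to and including the 39 week follow-up visit". The row "Concomitant Medication Assessment" in the Section 10.1 schedule runs throughout the study. Added therapies other than drugs are recorded in the subject diary (Section 10.2.13), which is reviewed at the 39 week visit.

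**The case against.** The discrepancy itself is hard to dispute. The arguments on the other side concern its weight and the supporting points.

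- **The SAP may not contradict itself.** Its exploratory scope is permissive: comparisons up to week 39 may be presented, and a 12-week endpoint fits inside that range. This stands. The firm conflict is between SAP and protocol; the SAP's own scope only makes a deliberate 12-week cut-off less likely.
- **The SAP may have inherited the number.** SAP 1.0 says that it follows the original final protocol, whose failure definition cannot be seen here. But SAP 3.2 includes the function, stiffness, total WOMAC and rescue endpoints that the protocol's change table shows as added in version 2.0. In substance the SAP follows the current protocol. If the 12 was inherited, it is out of date and still needs correcting.
- **The data may be thinner than needed.** Section 10.2.12.3 covers medications only, so procedures rest on the diary. That section also starts the record at consent, and Section 10.2.1 requires extension consent only before the 39 week visit, so collection between week 26 and a late consent is not clearly covered. This stands as a caution about completeness. It does not justify discarding weeks 12 to 26, which lie within Cingal 16-02, or the extension data that are collected.
- **The modelled share is wide.** At 10% to 60% across timing assumptions it cannot be read as an estimate. This also stands. The figures that rest on the documents alone are 27 of 39 weeks and 3 of 7 visits.
- **The endpoint is exploratory and its presentation optional.** Concomitant medications are also tabulated by arm (SAP 4.3). This limits the consequence but does not remove the error.

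**Conclusion.** The concern holds. SAP 4.1.4 states the wrong end of the failure window relative to the protocol that it implements. Followed exactly, it drops 69% of the follow-up time and 3 of 7 follow-up visits from the failure count and its test. These figures need no assumption. The share of failures lost depends on their timing, which the documents do not give: about two thirds under a constant hazard, with the failure proportion by week 39 assumed to be 5% to 30% and every subject followed.

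The consequence is confined to one exploratory endpoint. Sample size, power, Type I error control and all primary and secondary analyses are unaffected. The SAP should be corrected before the analysis is run.

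**What to change.** In SAP 4.1.4, change the end of the treatment failure window from the 12 week to the 39 week visit and leave the rest of the definition as it is. It then matches Protocol Sections 2 and 12.1.3.

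In the failure table, show for each arm the number of subjects followed to weeks 12, 26 and 39. Subjects who finish Cingal 16-02 "will have the option to participate in the sub-study", so after week 26 failure status is known only for those who join. The 39-week count will be incomplete for the others, and the denominators make that visible.

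The cost is one number in one sentence and a few table rows. No new medication data are called for. Before programming, confirm that procedures on the index knee, and any treatment between week 26 and extension consent, can be retrieved from the diary and case report form.

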12.6 Additional Analyses

All of the analyses are performed on the data without covariates or other factors assumed in the model. If it is determined that certain factors may influence the outcomes of the endpoints, then additional analyses will be performed. For the continuous variables, the factors will be added to the ANOVA model and evaluated in a stepwise fashion for significance. For the discrete variables, the data will be analyzed via a GEE model with the factors added to the model.

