4.1.3 Secondary Efficacy Endpoints

There are multiple secondary endpoints. In order to preserve the integrity of the Type I error, these will be tested in a hierarchical manner. The order of the testing is as the order presented here.

The change from baseline in knee pain as measured by the WOMAC Pain Score (100 mm VAS) at 39 weeks post treatment comparing the Cingal group to the TH group.

This secondary efficacy endpoint is the change from baseline in knee pain as measured by the WOMAC Pain Score (100 mm VAS) at 39 weeks post treatment comparing the Cingal group to the TH group.

Data will be analyzed via an analysis of variance (ANOVA) with a term for treatment and baseline pain score as a covariate. The primary hypothesis will be tested by a predefined contrast for comparing the Cingal group to the triamcinolone hexacetonide group. Formally, the hypothesis to be tested is:

$$H_0: \mu_{DC} = \mu_{DT} \text{ versus } H_A: \mu_{DC} \neq \mu_{DT}.$$

Where μ_{DC} is the mean change from baseline in the WOMAC Pain Score for the Cingal group at 39 weeks and μ_{DT} is the mean change from baseline in the WOMAC Pain Score for the triamcinolone hexacetonide group at 39 weeks. Since there are three treatment groups in this study, this hypothesis will be tested using a one way ANOVA and constructing a contrast for this hypothesis. This process is the same as using a baseline pain adjusted two-sample t-test with the common variance estimate from the ANOVA.

The anticipated SAS code for this analysis is given as:

The mean difference will be estimated and tested using the contrasts from PROC GLM on the responses at the 39 week time period.

```

PROC GLM DATA=EFF;
  WHERE VISITNO = 39;
  CLASS TRT;
  MODEL WOMODIFF = BASEWOM TRT / TYPE3 ALPHA=0.05;
  ESTIMATE 'CINGAL VS MONOVISC' TRT 1 -1 0 ;
  ESTIMATE 'CINGAL VS TH'      TRT 1 0 -1 ;
  ESTIMATE 'MONOVISC VS TH'    TRT 0 1 -1 ;
  LSMEANS TRT / DIFF CL ALPHA=0.05;
  FORMAT TRT TRTF. ;
  RUN;

```

In this model, the WOMODIFF is the difference in WOMAC Pain Scores from baseline. The variable TRT is a categorical variable where 1 = Cingal, 2=Monovisc, and 3=TH. The variable

BASEWOM is the baseline WOAMC scores and the variable VISITNO is the visit number identifier. ODS statements will be used to output the contrasts and the mean differences into data sets that can be easily displayed using PROC REPORT. The primary analysis will be comparing Cingal to TH.

The tables for this analysis will be displayed as:

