Data will be analyzed via an analysis of variance (ANOVA) with a term for treatment and baseline Total WOMAC score as a covariate. The hypothesis will be tested by a predefined contrast for comparing the Cingal group to the TH group. Formally, the hypothesis to be tested is:

$H_0: \mu_{DC} = \mu_{DT}$ versus $H_A: \mu_{DC} \neq \mu_{DT}$.

Where μ_{DC} is the mean change from baseline in the Total WOMAC Score for the Cingal group at 39 weeks and μ_{DT} is the mean change from baseline in the Total WOMAC Score for the TH group at 39 weeks.

The change from baseline in the Patient Global Assessment at 39 weeks post treatment comparing the Cingal group to the triamcinolone hexacetonide group.

Since this is a secondary endpoint the data will be analyzed for each time point individually with no adjustment for multiplicity. Data will be analyzed via an analysis of variance with a term for treatment and baseline PGA score as a covariate. The primary hypothesis will be tested by a predefined contrast for comparing the Cingal group to the Triamcinolone Hexacetonide group. Formally, the hypothesis to be tested is:

$H_0: \mu_{DC} = \mu_{DT}$ versus $H_A: \mu_{DC} \neq \mu_{DT}$.

Where μ_{DC} is the mean change from baseline in the Patient Global Assessment Score for the Cingal group and μ_{DT} is the mean change from baseline in the Patient Global Assessment Score for the triamcinolone hexacetonide group. Since there are three treatment groups in this study, this hypothesis will be tested using a one way ANOVA and constructing a contrast for this hypothesis. This process is the same as using a two-sample t-test with the common variance estimate from the ANOVA.

The mean difference will be estimated and tested using the contrasts from PROC GLM on the responses by week with the 39 week time period being the time point of interest for the analysis of this secondary endpoint.

4.1.3.4 The change from baseline in the Evaluator Global Assessment through 39 weeks post treatment comparing the Cingal group to the triamcinolone hexacetonide group.

Since this is a secondary endpoint the data will be analyzed for each time point individually with no adjustments for multiplicity. Data will be analyzed via an analysis of variance with a term for treatment and baseline EGA score as a covariate. The primary hypothesis will be tested by a predefined contrast for comparing the Cingal group to the triamcinolone hexacetonide group. Formally, the hypothesis to be tested is:

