4.6 ADDITIONAL ANALYSES

All of the analyses are performed on the data with the specified covariates or other factors assumed in the model. If it is determined that certain factors may influence the outcomes of the endpoints, then additional analyses will be performed. For the continuous variables, the factors will be added to the ANOVA model and evaluated in a stepwise fashion for significance. For the discrete variables, the data will be analyzed via a GEE model with the factors added to the model.

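### The exploratory model for EQ-5D, range of motion and WOMAC at visits other than week 39 names no baseline covariate and does not say whether change or raw score is analysed

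*SAP*

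**What the plan says.** SAP 4.1.4 covers any comparison and any visit not already a primary or secondary endpoint, and lists EQ-5D, range of motion, the WOMAC scores and the global assessments among others. Its only model statement for continuous data is that "the continuous variables will be analyzed via an analysis of variance and contrasts used to assess the prescribed comparisons". Protocol 12.1.3 carries the same sentence.

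The secondary endpoints are treated differently. For WOMAC pain, SAP 4.1.3 says: "Data will be analyzed via an analysis of variance (ANOVA) with a term for treatment and baseline pain score as a covariate". Physical Function, Stiffness and Total WOMAC each get their own baseline in the same way. All four are defined at 39 weeks, and the specimen pain code keeps only the week-39 records.

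For the Patient Global Assessment, SAP 4.1.3 gives an "analysis of variance with a term for treatment and baseline PGA score as a covariate", run with "PROC GLM on the responses by week with the 39 week time period being the time point of interest". For the Evaluator Global Assessment, "the data will be analyzed for each time point individually with no adjustments for multiplicity", "with a term for treatment and baseline EGA score as a covariate".

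Two general statements bear on the silence in 4.1.4. SAP 4.6: "All of the analyses are performed on the data with the specified covariates or other factors assumed in the model". Protocol 12.6: "All of the analyses are performed on the data without covariates or other factors assumed in the model".

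**The concern.** Wherever the SAP wants baseline adjustment for a secondary endpoint, it names the covariate. In 4.1.4 it names none. The natural reading is an unadjusted comparison for EQ-5D, for range of motion, and for WOMAC at visits other than week 39. One WOMAC pain table could then show a baseline-adjusted estimate at week 39 beside unadjusted ones at weeks 1 to 26.

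The response is also left open. SAP 4.2 defines the baseline to be used when a change is calculated, but nothing says that the exploratory endpoints are analysed as change. Whoever programs the tables must choose both the response and the covariate, possibly with treatment codes in hand.

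Three things are at stake: interval width, chance imbalance at baseline (mainly in comparisons with the TH arm), and comparability of estimates across visits. The baseline values needed already exist. The Protocol 10.1 schedule has EuroQol, range of motion, WOMAC and both globals at Baseline, and Protocol 10.2.1 carries the Cingal 16-02 baseline data into this study.

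**Working it through.** **Where the gap lies**

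| Endpoint | Week 39 | Other visits |
|---|---|---|
| WOMAC Pain, Function, Stiffness, Total | Own baseline (SAP 4.1.3) | SAP 4.1.4 only: no covariate named |
| Patient and Evaluator Global | Own baseline (SAP 4.1.3) | Own baseline, by time point (SAP 4.1.3) |
| EQ-5D, range of motion | SAP 4.1.4 only | SAP 4.1.4 only |

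**Inputs.** Arms of 256, 256 and 64, and an SD of 20 mm (Protocol 12.1). The sizing comparison is on change, so I take 20 mm as the SD of change. Two quantities are not in the documents and are assumed: the baseline-to-visit correlation r, and k, the baseline SD divided by the follow-up SD.

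**The plan's own figures reproduce.** For Cingal against TH (10 mm, SD 20, 90% power, two-sided 5%, 2:1), TH needs 1.5 × (1.960 + 1.282)² × 20²/10² ≈ 63.0, rounded up to 64. The t-based value is 63.7, also 64, which gives 128 on Cingal. For Cingal against Monovisc (5 mm, SD 20, 80% power), the t-based value is 252.1, so 253 per group. Both match Protocol 12.1.

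**Precision.** Relative to ANCOVA, the variance of a between-arm contrast is

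- unadjusted change: (1 + k² − 2rk)/(1 − r²), which equals 1 + (k − r)²/(1 − r²);
- unadjusted raw score: 1/(1 − r²).

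The first form shows that the loss is never negative and disappears when k = r. With k = 1 it becomes 2/(1 + r).

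| r (assumed) | Change, k = 1 | Change, k = 0.6 | Change, k = 0.5 | Raw score |
|---|---|---|---|---|
| 0.3 | 1.54 | 1.10 | 1.04 | 1.10 |
| 0.5 | 1.33 | 1.01 | 1.00 | 1.33 |
| 0.6 | 1.25 | 1.00 | 1.02 | 1.56 |

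The k = 1 change-score formula was checked by simulating 4,000 trials with the plan's arm sizes. ANCOVA variance over unadjusted variance came out at 0.67, 0.73 and 0.87 for r = 0.3, 0.5 and 0.7, against 0.65, 0.75 and 0.85 from theory.

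**In millimetres (k = 1, SD of change 20).** The standard error of Cingal minus TH is 20 × √(1/256 + 1/64) = 2.80, so the unadjusted 95% half-width is 1.96 × 2.80 ≈ 5.48 mm. With the covariate it is 5.48 × √((1 + r)/2): 4.42 mm at r = 0.3 and 4.90 mm at r = 0.6.

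**Chance imbalance.** The standard error of the baseline mean difference is √(1/256 + 1/64) = 0.14 baseline SDs for Cingal against TH, compared with √(2/256) = 0.09 for Cingal against Monovisc. The TH comparisons are the more exposed.

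**Which k is plausible.** For WOMAC pain, Protocol 9.1.4 restricts baseline to 40 to 90 mm, while follow-up scores are unrestricted. A k below 1 is therefore credible for that score, and the k = 1 column may overstate its loss. No such entry window is set for EQ-5D. Range of motion has only a flexion minimum, in Protocol 9.1.5.

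**The case against.** The best reply is that 4.1.4 is silent rather than unadjusted. This SAP uses the term ANOVA for models that contain a baseline covariate, and even calls the adjusted pain model a one-way ANOVA. SAP 4.6 could be read as carrying the 4.1.3 covariates throughout. That much stands: the text does not rule adjustment out. But each adjusted model in 4.1.3 names its covariate, SAP 4.3 uses the same term for a plain one-way comparison, and Protocol 12.6 says no covariates. Under either reading the model needs stating.

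Four stronger readings are tempting, and the documents do not support them.

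- **That the global assessments at other visits are also unadjusted.** SAP 4.1.3 analyses both at each time point with their own baseline. (Protocol 12.1.2 names baseline pain as their covariate, which is still an adjustment.)
- **That SAP 4.6 forbids covariates beyond those specified.** It contains no such restriction and goes on to allow factors to be added.
- **That a fixed share of the subjects is thrown away.** Any such figure depends on r and k, and the documents give neither.
- **That the Cingal 16-02 results at weeks 1 to 26 will be unadjusted.** That trial's own analysis plan is not among these documents. The point concerns only how those visits are presented here.

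It is also fair to say that these analyses are exploratory and optional, and that an unadjusted comparison of randomised arms is valid.

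**Conclusion.** The point holds as a gap in specification with a possible loss of precision. For EQ-5D, range of motion, and WOMAC away from week 39, the plan names no baseline covariate and does not fix the response. Its two general statements on covariates disagree, and Protocol 12.6 also contradicts the adjusted models in Protocol 12.1.2.

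Over correlations of 0.3 to 0.6, the variance penalty is 1.25 to 1.54 for unadjusted change with equal SDs, and 1.10 to 1.56 for an unadjusted raw score. For change it falls to between 1.00 and 1.10 if the baseline SD is about half to six-tenths of the follow-up SD. All of these rest on assumed values.

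The consequence is small. The primary Fisher's exact test, the secondary analyses and the sample size do not depend on it. This is an improvement available without cost, not a defect that threatens a conclusion.

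**What to change.** Add to SAP 4.1.4 and Protocol 12.1.3: *Between-group comparisons of continuous exploratory endpoints that have a baseline measurement are analysed as change from baseline, with treatment and the endpoint's own baseline value as covariate.*

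The limits in that sentence are deliberate. Section 4.1.4 also covers within-group comparisons and rescue-medication pill counts, which the plan compares descriptively, and a broader sentence would not fit either.

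Also amend Protocol 12.6 so that it agrees with SAP 4.6 and with the covariates in Protocol 12.1.2.

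The cost is one sentence in each document and one correction in the protocol. No new data are needed. The wording should be settled before treatment codes are available to the analysts.
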